## Introduction to Proposal

We greatly appreciate the reviewers' feedback and respond here to the weaknesses noted. The review highlighted favorably the public health significance and innovative features as well as strengths of the investigative team and environment.

- 1. Clarify importance of screening for child maltreatment (CM) in primary care, feasibility of implementing SEEK.** SEEK targets major risk factors for CM, rather than directly screening for the problem. Over 7 million children are reported annually for CM, with many costly consequences for individuals, families and society. Relationships between primary care professionals (PCPs) and parents offer an excellent opportunity for prevention by addressing targeted psychosocial problems. There is mounting interest in addressing social determinants of health; it is a priority of the American Academy of Pediatrics (AAP). SEEK was developed with replication in mind. Neighborhood health center pediatricians gave input, while recognizing time constraints in busy practices. SEEK II was effective in 18 private practices and has been implemented in over 100 practices, confirming its feasibility.
- 2. Changes to the SEEK model, “not really implementation of an evidence based practice.”** We clarified that the core components of SEEK remain. This project examines effectiveness of new implementation (not intervention) strategies to facilitate scale-up of the evidence-based SEEK model.
- 3. Need to measure CM to assess SEEK’s impact.** We added a specific aim (Aim 3) in this regard and a measure of CM-related ICD-10 codes from EHRs for all children 0-5 in all the participating practices.
- 4. On-line training not effective in changing practitioner behavior, and limited role of CME.** This project builds upon growing support for online training's effectiveness when blended with interpersonal modalities such as webinars and collaborative learning; these are included in our MOC approach. It is convenient for learners and responds to the increasing need for student-centered versus instructor-centered learning. This study offers a good opportunity to examine the impact of this learning approach on PCP behavior. We agree that CME credits are a minor incentive, but it is still worth offering.
- 5. Need to better describe Implementation strategies, theoretical or empirical support regarding them, and mechanisms for change.** The training and implementation strategies are both more clearly described and rationalized. These were guided by social cognitive theory. For example, role plays demonstrate how PCPs can address a targeted problem. Implementing the approach in one's practice and participating in collaborative learning via webinars further foster self-efficacy. The transtheoretical model helps PCPs use Motivational Interviewing to plan jointly with parents. By addressing psychosocial problems, SEEK aims to support parents, strengthen families, promote children's health and safety, and thus prevent CM.
- 6. Need to better address risk of improved screening and detection of CM.** SEEK only screens for risk factors rather than for CM. Our experience in 2 RCTs and with over 100,000 families has been that CM very rarely emerges as a concern – when discussing discipline. This is similar to what PCPs typically encounter in practice. The only direct contact between the researchers and parents is in the qualitative interview; we have developed our response to detecting possible CM then (see Human Subjects).
- 7. Develop data analysis re. parent and EHR data, and power analyses.** We now provide more details on analysis of the parent and EHR data, and more detailed power calculations. We also address the comparison of the SEEKonline vs. the Traditional paper and pencil implementation strategies and implementation outcomes. Limitations to our design, and the rationale for allowing selection versus randomization of service delivery facilitation (i.e., SEEKonline vs. Traditional) are described.
- 8. Need questions of PCPs specific to SEEK.** We clarify in our Measures section, several assessments of PCP perceptions specific to SEEK. The PCPQ probes thinking and practice related to the targeted problems. The PCP survey assesses their experience implementing SEEK. We also evaluate their training experience, and qualitative interviews will probe in depth their experience delivering SEEK.
- 9. Focus on online training not innovative.** We cut this as an innovation. However, despite being popular, there has been rather little evaluation of the effectiveness of this modality in physician training.
- 10. Efficacy of SEEK uncertain, no tests of effectiveness.** The 2nd RCT in 18 private pediatric practices demonstrated SEEK's effectiveness. Findings replicated key findings from the initial efficacy trial. The current study aims to evaluate SEEK's effectiveness under two different training conditions as part of a Hybrid III effectiveness trial. SEEK's effectiveness has been recognized by the Centers for Disease Control and Prevention, the U.S. Agency for Healthcare Research and Quality, the AAP and the California Evidence-Based Clearinghouse as a top tier prevention model with a strong evidence base.
- 11. Confusion re. observational vs. experimental design.** We have made clear that the training strategies will be randomized, and that practices will choose between SEEKonline and the Traditional implementation strategy. Some measures involve observation of SEEK's implementation.

## Specific Aims

Child maltreatment (CM) is a major public health problem, affecting many lives, in the short-and long-term, and costing individuals, families and our society dearly. In 2015, CM reports were made to child welfare on 7.2 million children. The Healthy People Goals 2020 call for reducing fatal and nonfatal CM. A U.S. Surgeon General called for making the prevention of CM a national priority. Achieving this goal hinges on the broad implementation of evidence-based interventions, including in healthcare systems. One evidence-based practice

(EBP) is the Safe Environment for Every Kid (SEEK) model, developed for pediatric primary care, and recognized by the CDC, AHRQ, the AAP and the California Evidence-Based Clearinghouse. Primary healthcare offers an excellent opportunity to help address prevalent psychosocial problems (e.g., parental depression) that are risk factors for CM. By helping address targeted psychosocial problems, SEEK can strengthen families, support parents, and help build safe, stable and nurturing relationships. These promote children's health, development and safety, help prevent CM, and benefit the health of the US population.

Despite its evidence-base, SEEK has not been widely adopted, leaving a large gap for the prevention of CM. To date only about 100 primary care clinics have adopted SEEK. To facilitate SEEK's uptake, we aim to test the effectiveness of two pragmatic training strategies, while retaining the core elements of the model. Medical practitioners are increasingly engaged in distance learning, such as online offerings. Most often these are self-directed efforts such as viewing a presentation. However, recently online trainings with more interactive modalities such as webinars and guidance during an introductory period have become popular. One example is the Maintenance of Certification (MOC) quality improvement (QI) project for SEEK, approved by the American Boards of Pediatrics and of Family Medicine for this purpose. The effectiveness of this collaborative learning approach vs. self-directed training regarding SEEK's implementation has yet to be evaluated.

To further facilitate ease of adoption, *SEEKonline* was developed to assist primary care professionals (PCPs) deliver the model consistently, with fidelity. This software guides PCPs through the steps of SEEK during a regular primary care visit, enables parents and PCPs to participate electronically, offers real time decision support and facilitates documentation. The effectiveness of this software in facilitating start-up and delivery with fidelity, relative to the "Traditional" paper and pencil approach (as in the original RCTs) has not yet been examined. In addition, a third of US children receive their primary care from family medicine practitioners, making it important to evaluate SEEK in these settings too.

**Proposed Study.** This randomized Type III hybrid design leverages a commitment by 5 major healthcare systems to implement SEEK, enabling a rigorous evaluation of implementation strategies to optimize the adoption and delivery of SEEK in primary care settings, and subsequent prevention of CM: the (1) independent online (IND)versus in-depth structured (MOC) training and (2) use of *SEEKonline* vs. the Traditional approach to guide fidelity of model delivery. Further, SEEK will be examined in pediatric and family medicine settings, increasing the generalizability of findings. As in PAR-16-238, this proposal targets "strategies to implement health promotion, prevention, screening, early detection, and diagnostic interventions, as well as effective treatments, clinical procedures, or guidelines into existing care systems" through these aims:

**Aim 1: Evaluate the effectiveness of targeted implementation strategies on the implementation of SEEK in primary care settings.** PCPs will be randomly assigned to one of two training conditions (IND or MOC). **H1.** MOC training will lead to more positive attitudes, comfort level and competence in addressing risk factors for CM. **H2.** Users of *SEEKonline* will deliver the intervention more often, achieving a higher rate of penetration, and will report higher levels of provider and parent satisfaction than the Traditional mode of delivery. **H3.** MOC training and *SEEKonline* will together optimize adoption and sustainment of SEEK.

**Aim 2. Evaluate the impact of inner context variables (e.g., variation between pediatric and family medicine) on the SEEK implementation process and understand associated barriers and facilitators to successful service start-up and sustainment of SEEK delivery.** Using a mixed methods approach, standardized measures of the implementation process (Stages of Implementation Completion; SIC) and associated cost (Cost of Implementing New Strategies; COINS), will be integrated with qualitative interview data focusing on barriers and facilitators during implementation from exploration to sustainment. Variations in adoption, model fidelity, and sustainment, and the economic ramifications of each of the SEEK training and implementation strategies will be examined.

**Aim 3. Examine the effectiveness of the intervention strategies in preventing CM.** CM will be measured via prevalence of ICD-10 codes related to CM obtained from electronic health records for all children 0-5 attending the practices. **H1.** Incidence of CM will be reduced in practices after implementing SEEK. **H2.** Practices randomized to MOC training that successfully implement SEEK, will have lower incidences of CM than with the IND approach. We will also probe the influence of *SEEKonline* and the Traditional approach on CM rates. Additionally, implementation success, will be examined in relation to CM prevalence rates.

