### **Implementation Process and Outcomes**

The **Stages of Implementation Completion (SIC)** is an observational assessment tool developed in a large randomized implementation trial. The SIC has 8 stages, each including sub-activities, extending from Engagement with the developers to achievement of practitioner Competency. Each stage maps onto 3 phases of implementation (Pre-Implementation, Implementation and Sustainment). Competency is viewed as *entering* into the Sustainment phase. Sustainment is an ongoing process toward achievement of Stage 8.

The SIC has been adapted for over 20 different implementation strategies involving varied interventions. These multiple adaptations led to the development of the empirically derived *Universal SIC*, with items found to be relevant and reliably utilized across each of the adaptations, regardless of service sector or population (e.g., child welfare, primary care, prevention). The Universal SIC spans the 8 original SIC stages, with 45 activities tracked during implementation. For the current study, completion of activities will be monitored by the practice manager and collected monthly by the research team, with data entered into the SIC data collection website. The website is managed by the SIC team, and through a web-based tool, implementation performance at the practice level can be benched against other implementation efforts.

**SIC Scores.** Three scores are calculated for each SIC stage. First, the time that a practice takes for a stage is calculated (Duration Score). Because the implementation process is nonlinear, the Duration Score takes into account activities that may not be completed sequentially within a stage. If a site completes only one activity in

a stage, the Duration Score for that stage is a single day. Duration Scores are calculated separately for each stage due to the potential for overlap across stages; the total Duration Score does not necessarily equal the summation of each stage's Duration. Rather, the total Duration Score is calculated from the date of the first completed SIC activity to the final activity completed, regardless of the stage in which it occurred. Second, the percentage of activities completed within a stage is calculated Proportion Score). Similar to Duration,

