## **Data Analysis Plan**

**General Considerations.** Standard statistical methods for calculating point estimates, confidence intervals, and p-values require the assumption of independence. However, due to participants being clustered within healthcare systems and within practices, this assumption cannot be made. To account for the lack of independence among multiple measures within the same system or practice, we will use random effects (i.e., hierarchical) models. In these models, we will include a random effect for system and for practice. In analyses involving multiple measures from the same person, we will include a random effect for each one. These models can be fitted using SAS Proc GLIMMIX, which fits models for both quantitative and binary outcomes. There will be diverse analyses based on the data. Below we highlight the main analyses for each Aim. The qualitative data (see below) will inform the models through processes of convergence (i.e., triangulation) and expansion (i.e., explanation of unexpected findings from analyses of quantitative data).

Sex as a biological variable will be considered across multiple levels of analyses. At the PCP, parent, and child levels of analyses, there is the potential for variation in implementation outcomes related to sex. Analyses will include a test for sex differences; when differences are noted, additional analyses will examine the influence of additional contextual factors on these outcomes.

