**Aim 1. Compare alternative approaches to implementation of SEEK with respect to clinical and implementation outcomes.** To address aim 1a, we will compare practices randomized to MOC to practices randomized to IND with respect to clinical and implementation outcomes. These include perceptions of the training from the PCPs' evaluations, scales from the SEEK PCPQ (e.g., Competence in addressing problems) and the PCP Survey (e.g., Ease of Delivery. We will also compare the groups with respect to rates of screening and parents' receipt of services and satisfaction with the PCP. For quantitative outcomes, statistical inference will be based on linear regression models; for binary outcomes, inference will be based on logistic regression models, accounting for repeated measures within PCP and system. For example, for PCPs reported Competence we will fit this model:  $E(\text{Competence}_{ijkl}) = \beta_0 + s_i + p_j + i_k + \beta_1(\text{POST}) + \beta_2(\text{POST})(\text{MOC-4})$  where Competenceijkl stands for the competence score measured at the lth time point (l=1 or 2 for baseline or follow-up respectively) of the kth PCP in the jth practice of the ith system, and  $s_i$ ,  $p_j$ ,  $i_k$  are random effects for system, practice and PCP respectively; POST=1 if it is a post-training measure and 0 otherwise, MOC = 1 if the PCP was trained using MOC and 0 if IND, and  $\beta$ 's are parameters to be estimated. Note this model assumes that the mean baseline scores are the same in both groups, as recommended for randomized studies. This model can be fitted using restricted maximum likelihood. To avoid possible biases due to selective attrition from the training, the primary analysis will follow the "intention to treat" principle including all those randomized. Secondary analyses will be based on groups defined by training received. To address Aim 1b we will compare practices who choose SEEK-online to practices who choose the traditional approach using the same statistical methods as described for Aim 1a. Outcomes of interest will include staff satisfaction, costs, rates of screening, receipt of services, and parental satisfaction.

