**Aim 3. Examine the effectiveness of SEEK in reducing CM.** As in our previous studies, we will identify CM-related diagnoses, now via EHRs. We will review the EHR for each child (0-5) in each practice for two years prior to implementing SEEK and during implementation. The presence of CM-related ICD-10 codes will be recorded. The proportion of children with CM diagnoses before and during SEEK will be compared at each practice. Formal inference regarding the best estimate and statistical significance of pre-post differences will be based on a binary regression model with a random effect for site, similarly to Aim 1.

**Sample Size Considerations.** Our projected sample sizes (numbers of practices, professionals within each practice, and children in the practices) should provide good precision to estimate parameters and ample power to detect moderate associations. Table 4 below shows the detectable effect sizes for various comparisons, based on performing 2-sided .05-level tests and incorporate a 1.5-fold increase in variance and sample size to account for potential loss of power due to clustering of observations within practices and systems. In general, the detectable effect sizes are moderate, at plausible levels. We observed effect sizes of about 1.0 regarding Competence and Comfort in SEEK II. For Aim 2, assuming 90% of practices provide organizational information, we will estimate the rate of adoption of SEEK accurately,  $\pm$  15 percentage points.

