**Table 4. Power Calculations**

Aim	Respondents/Source	Measure	N per group	Detectable Effects with 80% power
1a	PCPs	Changes in Comfort and Competence in addressing CM	137	Effect size  of 0.42
1a	Parents	Parent satisfaction	144	Effect size  of 0.41
1b	Staff	Staff Perceptions	24/72 	Effect size  of 0.82
2	Practices	Proportion adopting	59	Precision of +/- 15 pct points
3	EHR	Pre-post prevalence of CM-related diagnoses	98,000	5% vs. 4.5%  10% vs. 9.6%

Defined as the difference in means between groups divided by the standard deviation.

Conservatively assuming an imbalance between SEEKonline vs. Traditional of as much as 25% to 75%.

In our previous evaluations of SEEK, we observed rates of CM in the medical record ranging from 5% to 1%.

methods.

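### Aim 3 H2, the only child-maltreatment hypothesis that uses the MOC-vs-IND randomisation, is conditioned on successful implementation after randomisation, with no success cut-off and no stated MOC-vs-IND analysis

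*Combined protocol and SAP*

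**What the plan says.** Practices are randomised to MOC or IND training, and they choose SEEKonline or Traditional delivery for themselves (Strategy and Design Overview). Aim 3 in the Specific Aims has two CM hypotheses. H1 is a before-after comparison. H2 is the arm comparison: "Practices randomized to MOC training that successfully implement SEEK, will have lower incidences of CM than with the IND approach". The same paragraph then adds a separate question: "Additionally, implementation success, will be examined in relation to CM prevalence rates".

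The Aim 3 part of the Data Analysis Plan starts from complete data: "We will review the EHR for each child (0-5) in each practice". It compares CM proportions before and during SEEK, and the "statistical significance of pre-post differences will be based on a binary regression model with a random effect for site, similarly to Aim 1". It writes down no training-arm term, no arm-by-period term and no rule for which practices enter an arm comparison. The only Aim 3 row in Table 4 is "Pre-post prevalence of CM-related diagnoses".

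Intention to treat is stated under Aim 1, where the primary analysis follows that "principle including all those randomized. Secondary analyses will be based on groups defined by training received". The example model there contains a POST x MOC term.

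The nearest measure of success is the Stages of Implementation Completion (SIC): "Three scores are calculated for each SIC stage". The Aim 2 analysis summarises completeness by the final stage attained (0 to 8). Neither section labels any level as success.

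**The concern.** A randomised comparison is protected because the groups are fixed before anything happens in the practices. H2 gives up that protection by keeping only practices that later succeed. On the most direct reading the filter applies to MOC alone, so the better-performing part of one arm would be set against the whole of the other. The wording is elliptical, though, and could also mean successful practices in both arms.

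Four analyses fit the text:

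1. all MOC against all IND;
2. successful MOC against all IND;
3. successful MOC against successful IND;
4. no arm test, only pre-post change.

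They answer different questions. SIC data are collected monthly, and the health-record extract comes in months 49 to 60. The analysis set and the meaning of success could therefore be settled after implementation results are known.

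**Working it through.** **1. Plan's own figure.** Inputs from Sample Size Considerations and Table 4: two-sided 0.05, 80% power, variance x1.5, 98,000 children per group. So z = 1.960 + 0.842 = 2.802 and v = 1.5 x p x (1 - p). For pre-post, with the two periods taken as independent, the detectable difference is z x sqrt(2v/98,000).

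- p = 5%: v = 0.07125, giving 0.338 points.
- p = 10%: v = 0.135, giving 0.465 points.

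Table 4 prints 5% vs 4.5% (0.5 points) and 10% vs 9.6% (0.4 points), so its Aim 3 row is not reproduced. The same inputs give 0.415, 0.404 and 0.809 for the effect-size rows, against 0.42, 0.41 and 0.82 printed, so they are read correctly. The mismatch is a separate matter. Below, both contrasts are computed on the same inputs.

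**2. Precision of the all-practice arm contrast.** Assume 1:1 allocation, 49,000 children per arm and no trend shared across practices. The difference in change between arms is detectable at z x sqrt(4v/49,000).

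| CM rate | Pre-post | MOC-vs-IND change |
|---|---|---|
| 5% | 0.338 points | 0.676 points |
| 1% | 0.154 points | 0.308 points |

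With the 90,000 children given under Sample, the 5% figures are 0.353 and 0.705.

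Selection costs further precision. If 60% of MOC practices are kept (29,400 children), the figure is z x sqrt(2v x (1/29,400 + 1/49,000)) = 0.780 points. With 60% of both arms it is z x sqrt(4v/29,400) = 0.872 points.

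**3. Bias from selecting on success, with no true effect.** Assumed, not in the documents: 24 practices per arm, 2,000 children each, 5% rate, practice-risk SD 0.3 (log), practice-trend SD 0.1 (log), and correlation rho between success and a falling CM trend. The trend SD matches Table 4's allowance. The sampling variance of log(post/pre) is 2 x 0.95/(0.05 x 2,000) = 0.019, and adding 0.1 squared gives 0.029, or x1.53.

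If the top share q on a standard normal success score is kept, the mean score of those kept is the normal density at the cut divided by q: 0.669 for q = 14/24, 0.966 for 40% and 0.350 for 80%. The mean log trend moves by -rho x 0.1 x that value.

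- MOC only, 14 of 24 kept: exp(-0.3 x 0.1 x 0.669) = 0.980; with rho 0.5, 0.967.
- Same share kept in both arms: the shifts cancel, ratio 1.00.
- Same rule, 40% of IND and 80% of MOC succeeding: exp(0.3 x 0.1 x (0.966 - 0.350)) = 1.019; with rho 0.5, 1.031.

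Simulation (8,000 runs per setting, t-test on practice log post/pre ratios) agrees and gives the error rates. Nominal is 2.5% in each direction.

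| Comparison | rho | Ratio | False findings |
|---|---|---|---|
| MOC only, 14 of 24 | 0 | 1.00 | 2.8% favouring MOC |
| MOC only, 14 of 24 | 0.3 to 0.5 | 0.98 to 0.97 | 4.9 to 7.9% favouring MOC |
| 14 of 24 in both arms | 0.3 to 0.5 | 1.00 | 2.5 to 2.6% favouring MOC |
| 40% of IND, 80% of MOC | 0.3 to 0.5 | 1.02 to 1.03 | 4.5 to 6.6% against MOC |
| All practices as randomised | 0.3 to 0.5 | 1.00 | 2.3 to 2.5% favouring MOC |

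Unequal success shares are a realistic case, because the Training section expects MOC to bring more efficient and competent adoption.

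**The case against.** The best defence is that the Aim 3 model is tied to Aim 1. That could carry over both the POST x MOC term and intention to treat, and Aim 1 compares the arms on clinical as well as implementation outcomes. The plan also warns that it is a summary: "Below we highlight the main analyses for each Aim". Records are reviewed in every practice, which fits an all-practice analysis. The trial is a Type III hybrid, so CM is not its main focus, and Aim 1's randomised comparison is properly stated.

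Much of this stands. A reader might infer that the investigators intend to discard unsuccessful MOC practices, or that the H2 result will be biased. The documents support neither. Leaving a term out of a summary is not a plan to select practices, the both-arms reading is open, and the bias depends on a correlation that the documents do not give.

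The defence does not close the gap. The link to Aim 1 qualifies a model for pre-post differences, Aim 1's listed outcomes do not include CM diagnoses, and its intention-to-treat sentence is about attrition from training. If the rule is carried over, including everyone randomised contradicts H2's own condition. H2 is also one of only two numbered CM hypotheses, so its test belongs among the main analyses.

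**Conclusion.** The point holds, and it should be fixed. The certain part is textual: a condition arising after randomisation in the only randomised CM hypothesis, no definition of success, and no stated arm contrast or power figure for it.

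The bias is conditional and modest. Under the assumed inputs, MOC-only selection produces a spurious ratio of about 0.98 to 0.97 and about 5 to 8% false findings favouring MOC. Equal shares kept in both arms produce none, a higher success share in MOC biases against MOC, and correlation 0 removes the bias. These figures show a mechanism and do not forecast this trial's result. A reader might also conclude that any success-based comparison flatters MOC; the direction depends on which of the readings is used.

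**What to change.** - Restate H2 for all practices as randomised.
- State in the Aim 3 analysis that H2 is tested by adding POST x MOC to the Aim 3 model, under the intention-to-treat rule already given for Aim 1.
- Add a MOC-vs-IND change row for CM to Table 4. On its inputs with 1:1 allocation and no shared trend, this is about 0.68 points at a 5% rate and 0.31 at 1%, against 0.34 and 0.15 for pre-post.
- Move the comparison of successful practices into the success analysis the Specific Aims already plan. Label it exploratory, define success in advance, use the same definition in both arms, and report the share succeeding in each, since unequal shares can bias it.

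The cost is wording and one power row. Counts before and during SEEK are already planned for all children 0-5 (Child Maltreatment measure; Procedures, Final 12 months).

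The downside is precision and dilution. On these inputs the all-practice contrast has twice the detectable difference of pre-post. If, as an assumption, 60% of MOC practices implement and only they have an effect, 0.676 points overall requires 0.676/0.6 = 1.13 points among implementers.
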